3 STUDY OBJECTIVE(S) AND DESIGN

3.1 Study Objective(s)

The objectives of this study are:

- To evaluate the efficacy of ASP0113 compared to placebo in reducing the incidence of CMV viremia (defined as plasma viral load ≥ 1000 IU/mL by central laboratory assay) through one year post first Study Drug injection in CMV-seronegative subjects receiving a kidney from a CMV-seropositive donor.
- To evaluate the safety of ASP0113 in CMV-seronegative subjects receiving a kidney from a CMV-seropositive donor.

3.2 Study Design

This is a randomized, double-blind, placebo-controlled trial which will enroll 140 CMV-seronegative recipients of kidney transplant from a CMV-seropositive donor at about 80 clinical sites. Subjects will be randomized at Day 30 \pm 3, in relation to the day of transplant, in a 1:1 ratio to ASP0113 or placebo, and stratified by use of anti-thymocyte globulin (ATG) prior to Randomization and by receipt of a kidney from a living or deceased donor. The active compound will be a vaccine (ASP0113) which contains two plasmids encoding gB and pp65 each at 2.5 mg/mL, formulated with CRL1005 poloxamer and benzalkonium chloride (BAK).

The placebo control will be phosphate-buffered saline (PBS). Subjects will receive either 5 doses of ASP0113 or placebo on Days 30 \pm 3, 60 \pm 5, 90 \pm 5, 120 \pm 5 and 180 \pm 5 in relation to the day of transplant (Day 0).

Injections should be administered only when there is no medical contraindication to an intramuscular (IM) injection. Syringes will be masked prior to dosing to blind the subjects and all other personnel who need to remain blinded to the treatment assignment (i.e., site staff other than pharmacy personnel and staff designated to administer Study Drug injections).

Starting within 10 days of transplant, subjects will have received prophylactic valganciclovir or ganciclovir (dose per package insert) through the day of Randomization to prevent CMV disease. (The subject can miss up to two valganciclovir or ganciclovir doses during this time period for any reason). Subjects will then continue to receive CMV specific CMV AVP with valganciclovir or ganciclovir (dose per package insert) to prevent CMV disease until 100 days post transplant. Subjects can have valganciclovir or ganciclovir interrupted, dose adjusted or replaced by other CMV-specific AVP per standard of care after the day of Randomization if renal function is compromised, there are toxicities related to the administration of the AVP or for any other medically indicated reason. In all subjects, plasma will be collected for central laboratory CMV viral load testing every two weeks from Day 100 through Day 200, then monthly through last Study visit Day 395.

In cases where CMV disease (CMV syndrome or CMV tissue-invasive disease) is suspected from the first Study Drug injection through Day 395, a local CMV viral load sample will be collected at the time of the first CMV symptom recognition.

Through Day 395, CMV-specific AVT should be initiated for CMV disease and can be initiated for CMV viremia based on the central or local laboratory results and standard of care at each institution. If CMV-specific AVT is initiated, a central CMV viral load will be obtained at a minimum of weekly from the time CMV-specific AVT is initiated until discontinuation. For cause CMV viral loads should be performed at a local lab approved by Astellas as Central lab viral load results will not be available in a timely manner to guide treatment decisions.

In addition, every time a sample is collected for a local CMV viral load, a plasma sample should also be collected and sent to the central laboratory for CMV viral load testing.

As one of the plasmids of the ASP0113 vaccine codes for the pp65 antigen, the theoretical possibility of interference with the pp65 antigenemia assay has been raised. At present, there are no data to suggest that such an interference occurs. However, to ensure subject safety and study integrity, sites that use pp65 antigen as their local methodology for the detection of CMV infection must adhere to the procedures defined below as a condition of participation in the trial:

- The local pp65 antigenemia results must be entered into the eCRF database within 72 hours (or next business day) of receipt to facilitate in-time monitoring of results.
- The Medical Monitor must be called within 48 hours (or next business day) if the pp65 antigenemia test is positive and the central laboratory PCR viral load result is negative.
- Both the pp65 antigenemia and the central laboratory test must be repeated within 48 hours of receipt of results, if the local pp65 antigenemia result is positive, the central laboratory PCR viral load result is negative and the subject is treated with CMV-specific AVT. Further treatment decisions are to be discussed with the Medical Monitor.

The plasmids in the Study Drug may interfere with certain PCR assays. If a PCR assay is used that amplifies the genes UL55/gB or UL83/pp65, this could result in either a false positive viral load or unblinding of the study subject.

Sites that are determined to have an unacceptable assay in their local lab but are able to determine a Sponsor- deemed acceptable work practice flow for utilizing another acceptable local assay or methodology will be allowed to participate in the trial. Note: Local CMV plasma viral load testing may be performed only at a local laboratory approved by the Sponsor.

Subjects will be followed for one year after first Study Drug injection (Primary Study completion/Day 395) for CMV viremia, CMV syndrome, CMV tissue-invasive disease, CMV-specific AVT, graft survival and subject survival.

Subjects will be followed for one year after the first Study Drug injection for resistance to valganciclovir or ganciclovir. Viral resistance will be assessed by a Central lab when there is no reduction in viral load two weeks after initiating valganciclovir/ganciclovir, when there is

no improvement in clinical signs and symptoms two weeks after initiating valganciclovir/ganciclovir or any time resistance to any CMV-specific AVT is suspected by the Investigator.

Immunogenicity to pp65 and gB will be assessed prior to Dose 1, two weeks after Dose 2, prior to Dose 3, two weeks after Dose 4, prior to Dose 5 and at the last study visit.

Subjects will be evaluated for local and systemic reactogenicity 15 minutes and one hour after each Study Drug injection and for 7 days by subject reporting via diary after each Study Drug injection.

Subjects will be contacted by telephone at 6 months after Day 395, then annually for the next 4 years to evaluate long-term safety related to the DNA vaccine. Items to be assessed by questionnaire and available patient records include mortality, development of any new malignancies, development of infection requiring hospitalization or resulting in death, graft survival, creatinine, and erythema and/or induration at the injection sites.

All adverse events (AEs) and serious adverse events (SAEs) will be collected from signing of the informed consent through one year post Study Drug injection. AEs occurring from signing of informed consent until just prior to the first dose of Study Drug, should be reported as a change in medical status or medical history. SAEs from the time of signing the informed consent will be recorded on the SAE worksheet and reported per Section 5.5.6. AEs reported after the first dose will be reported on the AE eCRF.

An independent Data Monitoring Committee (DMC) will be chartered to oversee the safety of subjects and review of the futility analysis. An Adjudication Committee (AC) will be chartered to adjudicate all cases of CMV syndrome, CMV tissue-invasive disease and CMV-specific antiviral therapy.

Two interim safety and efficacy analyses are planned. The first one will occur when 50 subjects (approximately 25 in each group) have completed the month 6 visit assessment. The second interim analysis will occur when 90 subjects (approximately 45 per group) have completed the 6 month visit assessment.

3.3 Randomization

At the Screening Visit, after the Informed Consent Form (ICF) has been signed, site staff will access the IRT system, enter the subject's required information, and the subject will receive a subject number assignment through the IRT for use throughout the study.

Subjects who subsequently meet the inclusion/exclusion criteria will be randomly assigned to receive either ASP0113 or placebo. The randomization to treatment will be equally allocated (i.e., 1:1) and stratified by the use of anti-thymocyte globulin and by receipt of a kidney from a living or deceased donor. The IRT vendor will generate the randomization schedule. To obtain the randomized treatment assignment for a subject, the pharmacist or designee will utilize an IRT system, which is available seven days a week, 24 hours a day.

Randomization is to be done after the completion of the Screening period, and at least 30 days \pm 3 after transplant day (Day 0). After submitting required information about the eligible subject, the drug kit number assignment will be provided.

Study Drug assignment will remain blinded to all site staff except the pharmacist and designated staff administering the Study Drug.

If a subject is randomized but does not receive Study Drug, the kit number will not be used again. In this instance, the treatment assignment should only be known by the pharmacist and designated staff (i.e., the blind must be maintained as it is with all other subjects).

4 SAMPLE SIZE

In a recent study of prophylactic valganciclovir given at 900 mg/day for 100 days to donor CMV-seropositive/recipient CMV seronegative (D+R-) kidney transplant recipients [Humar, 2006], CMV viremia, defined as CMV viral load \geq 1000 IU/mL, was seen through one year in 83 of 163 subjects [50.9%, 95% CI = (43.0%, 58.8%)]. In another study [Couzi, 2012], CMV infection, defined as two consecutive positive Polymerase Chain Reaction (PCR) assay results, was seen in 11 of 32 subjects (34.4%, 95% Confidence Interval (CI) = (18.6%, 63.2%)), respectively. Pooled from these two studies by weighted average, it is estimated that placebo rate is 46% (70% weight on Humar's result). A sample size of 64 subjects per arm will allow the study to have 80% power to detect a reduction in CMV viremia to 25% due to ASP0113 at 52 weeks using a 1-sided Chi-square test with a type 1 error rate of 5%. To allow for drop-out (randomized but not evaluable), 70 subjects per arm will be enrolled for a total sample size of 140 subjects.

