7.1 Sample Size

In a recent study of prophylactic valganciclovir given at 900 mg/day for 100 days to donor CMV-seropositive/recipient CMV seronegative (D+R-) kidney transplant recipients [Humar, 2006], CMV viremia, defined as CMV viral load > 600 copies/mL, was seen through one year in 83 of 163 subjects [50.9%, 95% CI = (43.0%, 58.8%)]. In another study [Couzi, 2012], CMV infection, defined as two consecutive positive Polymerase Chain Reaction (PCR) assay results, was seen in 11 of 32 subjects (34.4%, 95% Confidence Interval (CI) = (18.6%, 63.2%)), respectively. Pooled from these two studies by weighted average, it is estimated that placebo rate is 46% (70% weight on Humar's result). A sample size of 64 subjects per arm will allow the study to have 80% power to detect a reduction in CMV viremia to 25% due to ASP0113 at 52 weeks using a 1-sided test with a type 1 error rate of 5%. To allow for loss to follow-up, 70 subjects per arm will be enrolled for a total sample size of 140 subjects.

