7.9 Handling of Missing Data, Outliers, Visit Windows, and Other Information

The primary efficacy endpoint of CMV viremia is based on central laboratory assessments of CMV viral load which are taken every 2 weeks from Day 100 to Day 198, monthly from

Day 230 to Day 395 and all for cause (suspect CMV syndrome or CMV tissue-invasive disease) viral loads. In the primary efficacy analysis, subjects who are lost to follow-up will be imputed as having viremia. Otherwise, viremia will not be imputed in cases where central lab CMV viral load data are missing. Only observed viral loads meeting the definition of viremia will be counted.

However, secondary analyses of the primary endpoint will explore the consequences of alternative imputations. These will be described in the Statistical Analysis Plan.

The start and stop dates of AEs and concomitant medication will be imputed where necessary prior to unblinding. The imputed dates will be used to determine whether an AE is/is not treatment emergent. Listings of the AEs and concomitant medications will present the actual partial dates; imputed dates will not be shown.

Subjects who do not receive the Study Drug to which they have been randomized will be analyzed as treated for safety analysis and as randomized for efficacy analysis.

See the SAP for details of the definitions for windows to be used for analyses by visit.

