5.1 Full Analysis Set (FAS)

The Full Analysis Set (FAS) consists of all randomized subjects who received at least one dose of randomized study drug and who have at least one post dose viral load assessment within 1-year post first injection by central laboratory.

Specifically, the following will lead to a subject's exclusion from the FAS:

- Did not take study drug , or
- Had no viral load assessment by central laboratory after first study drug injection

The FAS will be the primary analysis set for efficacy analyses and for summaries of selected demographic and baseline characteristics. For this population, data will be analyzed by the treatment group that patients were randomized to.

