7.4 Analysis of Efficacy

7.4.1 Analysis of Primary Endpoint

7.4.1.1 Primary Analysis of Primary Efficacy Endpoint

The primary efficacy endpoint is the proportion of subjects with CMV viremia which is defined as plasma viral load ≥ 1000 IU/mL assessed by central assay through one year post first Study Drug injection. CMV viral load tests are scheduled once every 2 weeks for the first 8 tests starting 100 days from transplant and subsequently once per month for 7 more tests. In addition, a subject may have unscheduled tests (suspect CMV syndrome or CMV tissue-invasive disease) by the local laboratory so that the subject can be treated promptly with antiviral therapy (AVT) if needed. Everytime a local laboratory is performed, the sample should also be sent to the central laboratory for assessment. The CMV viral load collected from the central laboratory after first injection (Day 1) through day 380 ($=365+14+1$) that were collected as scheduled or unscheduled assessments will be utilized.

A patient who discontinue the study without a positive CMV viral load will be imputed as having a CMV viremia. A patient who has more than one time with viral load ≥ 1000 IU/mL by central assay will be counted once in this summary. Any unscheduled central laboratory values within the window will be included.

A Cochran-Mantel-Haenszel (CMH) test at the 1-sided 5% level stratified by use of anti-thymocyte globulin (ATG) and by receipt of a kidney from a living or deceased donor will be used to analyze the primary endpoint of CMV incidence rate.

The null and alternative hypotheses for this comparison are:

H0: Common Odds Ratio = 1.

H1: Common Odds Ratio < 1.

The odds ratio is defined as the ratio of odds of viremia in the ASP0113 group to that in the placebo group. The 1-sided p-value with the 2-sided exact 90% confidence interval for the

common odds ratio will be calculated (in SAS specifying the comor option in the exact statement of proc freq).

The primary analysis will be conducted for the FAS population.

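### The stated 80% power holds for 64 observed subjects per arm and an asymptotic test, but not if all 6 extra subjects per arm are counted as viremic (75-77%) or if the primary test is exact (76-78%)

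*SAP*

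**What the plan says.** **Sizing.** Both documents take a placebo rate of 46% and a vaccine rate of 25%. SAP 4 says "A sample size of 64 subjects per arm will allow the study to have 80% power to detect a reduction in CMV viremia" to that level, "using a 1-sided Chi-square test with a type 1 error rate of 5"%. Protocol 7.1 gives the same figures without naming the test.

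**The 6 extra per arm.** Protocol 7.1: "To allow for loss to follow-up, 70 subjects per arm will be enrolled for a total sample size of 140 subjects". SAP 4: "To allow for drop-out (randomized but not evaluable), 70 subjects per arm will be enrolled".

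**What happens to lost subjects.** SAP 5.1 removes from the FAS anyone who was not dosed or who "Had no viral load assessment by central laboratory after first study drug injection". On timing, SAP 7.4.1.1 says "CMV viral load tests are scheduled once every 2 weeks for the first 8 tests starting 100 days from transplant". For those who remain in the FAS, Protocol 7.9 says "In the primary efficacy analysis, subjects who are lost to follow-up will be imputed as having viremia", and SAP 7.9.1 repeats this. SAP 7.4.1.1 uses a different trigger: "A patient who discontinue the study without a positive CMV viral load will be imputed as having a CMV viremia".

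**The primary test.** Protocol 7.4.1.1 specifies a stratified CMH test with a 1-sided p-value and a 90% interval, and does not mention exact methods. SAP 7.4.1.1 also specifies CMH. It attaches the word exact to the 90% interval and ends the sentence that covers both p-value and interval by calling the COMOR option of the EXACT statement in PROC FREQ. SAP 7.4.3 then refers back to Section 7.4.1.1 as an exact CMH method. SAP 7.4.2 applies the same method to the secondary endpoints.

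**The concern.** The two sample-size sections give the same 6 subjects different fates. If they are not evaluable in the sense of SAP 5.1, they leave the analysis and 64 fully observed subjects per arm remain, which is the case that was sized. If they are lost to follow-up after a central result, they stay in and count as events. Dose 1 is at about Day 30 and routine central testing begins at Day 100, so losses can fall on either side of that line. Adding equal numbers of imputed events to both arms pulls the rates together, and neither sizing section allows for this.

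Separately, the trial is sized on a chi-square test, while the SAP can be read as testing with an exact method, which is more conservative. At stake are a power figure that describes only one combination of loss and test, and a primary p-value that can be read two ways. A borderline result could pass on one reading and fail on the other.

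**Working it through.** **Inputs.** Placebo rate 0.46, that is 0.7 × 83/163 + 0.3 × 11/32 = 0.4596 (Protocol 7.1, SAP 4). Vaccine rate 0.25. 1-sided alpha 0.05. 1:1 allocation. 64 or 70 per arm.

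**1. Reproduce the plan's figure.** Pooled-variance normal approximation, with mean rate (0.46 + 0.25)/2 = 0.355:

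n = [1.645 × √(2 × 0.355 × 0.645) + 0.842 × √(0.46 × 0.54 + 0.25 × 0.75)]² / 0.21² = 63.2, rounded up to **64**.

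Power at 64 is 80.5%, so the stated figure stands. The same formula with all 70 observed gives 83.5%.

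**2. Count lost subjects as viremic.** If k of 70 per arm are imputed, each rate p becomes ((70 − k)p + k)/70.

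- k = 3: (67 × 0.46 + 3)/70 = 48.3% and (67 × 0.25 + 3)/70 = 28.2%.
- k = 6: (64 × 0.46 + 6)/70 = 50.6% and (64 × 0.25 + 6)/70 = 31.4%. The difference falls from 21.0 to 19.2 points.

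**3. Power by full binomial enumeration.** This is unstratified. The CMH statistic uses its usual variance, and Fisher's test stands in for an exact CMH. Where two values appear, the first fixes the number imputed at exactly k and the second lets it vary at random.

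| Per arm | Asymptotic CMH | Exact (Fisher proxy) |
|---|---|---|
| 70 analysed, no loss | 83.1% | 78.4% |
| 64 analysed, all 6 leave the FAS | 80.4% | 76.0% |
| 70 analysed, 3 imputed, no other loss | 80.3% / 79.3% | 74.8% / 74.0% |
| 67 analysed, 3 leave and 3 imputed | 77.8% / 76.9% | 72.0% / 71.3% |
| 70 analysed, all 6 imputed | 77.3% / 75.6% | 71.3% / 69.8% |

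For all 6 imputed, the normal approximation gives 76.8% (fixed) and 75.1% (random), so 75-77% covers every method.

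**4. Stratified check.** With four near-equal strata, the same event rates in each, random imputation and 20,000 simulations, asymptotic and exact power are 83.6% and 78.9% with no loss, 80.9% and 75.8% at 64, and 75.1% and 69.2% with 6 imputed. The documents give no stratum sizes, so the strata are an assumption.

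**5. Actual test size at a common rate of 46%.** Asymptotic CMH: 4.6% at 64 per arm and 5.3% at 70. Fisher: 3.2% and 3.7%.

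**The case against.** **Nothing is miscalculated.** This stands. A reader might infer from the lower figures that the trial was wrongly sized or needs more patients. The documents do not support that: 64 is right for the test and the observed-data case that SAP 4 names.

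**All 6 imputed is a worst case.** This also stands. Protocol 6.1.1 keeps subjects who stop treatment in follow-up, and complete exit is specified only for withdrawal of consent. With 3 of 70 imputed and no other loss, power is still about 80%. So 75-77% is a lower bound for the planned loss under equal loss, not the expected power.

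**The SAP's loss wording already fits its analysis set.** Only partly. Both documents define an evaluable subject as one who is eligible and has had at least one injection. A dosed subject with no central result is therefore evaluable by definition but outside the FAS. The imputation triggers also differ: SAP 7.4.1.1 covers anyone who discontinues the study without a positive result, while SAP 7.9.1 and Protocol 7.9 cover only loss to follow-up and otherwise do not impute. The trigger decides how many subjects are counted as events.

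**The SAP already says exact.** The COMOR/EXACT clause and Section 7.4.3 do lean that way. They do not settle it: SAP 7.4.1.1 attaches the word only to the interval, and Protocol 7.4.1.1 and SAP 4 point to the asymptotic test.

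**The futility looks lower power further.** A reader might want to subtract a cost for them. The Appendix 2 formula, with interim rates equal to final rates, gives a 9.2% cumulative chance of stopping by the second look at 46% vs 25%. SAP Appendix 3, Table 2 reports 14.9%. Until these are reconciled, no cost can be stated.

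**Conclusion.** The point holds as a conditional-power and wording issue. The stated 80% is correct for 64 fully observed subjects per arm and an asymptotic test. Under the Protocol's own reason for the extra subjects, it falls to 75-77% if all 6 per arm are lost after a central result without a positive value. If the primary p-value is exact, 80% is not reached even before any imputation: about 76% at 64 per arm and about 78% at 70.

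These figures assume rates of 46% and 25%, the same rates in every stratum, and no futility stopping. They also assume equal loss in both arms, which matters: with 12 imputed in total, 7 vaccine and 5 placebo gives about 69%, and 5 and 7 gives about 84%. Those two values show the bias from unequal imputation and are not planning figures. The exact figures rest on an unstratified proxy, which the stratified simulation supports to within about 1 point. SAP 7.8 reports the futility analyses as already done, so resizing is not in question. The p-value can still be fixed, because SAP 1 places sign-off ahead of hard lock and unblinding.

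**What to change.** 1. **Sample-size text (Protocol 7.1, SAP 4).** Give one reason for the 6 extra per arm and say whether such subjects leave the FAS or are imputed. State asymptotic power as conditional: about 80% if all 6 leave the FAS, and 75-77% if all 6 are imputed, assuming equal loss. If amending the Protocol is impractical, a clarification in the SAP would serve. Use one imputation trigger in SAP 7.4.1.1 and 7.9.1. Do not add a futility cost until the stopping probabilities in SAP Table 2 are reconciled.

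2. **Primary p-value (SAP 7.4.1.1, with 7.4.3 made to match), before unblinding.** Choose one:
   - The asymptotic stratified CMH, which agrees with Protocol 7.4.1.1 and the sizing, with the exact 90% interval kept alongside. Cost: it gives up the guarantee of at most 5%, with actual size about 5.3% at 70 per arm and a 46% common rate.
   - The exact test, with power restated as about 76-78% before any imputation. Cost: about 4 to 5 points of power against the asymptotic test with no imputation, and about 6 with all 6 imputed.

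The choice carries over to the secondary endpoints through SAP 7.4.2. The cost is wording only; no extra patients are needed.
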